The primary aim of this observational prospective study is to evaluate, whether there is a difference in the blood flow, calculated as PI and RI in the arteriae uterinae right / left between women, undergoing HRT- or NC-cycle for FET. Measurements on the day of cycle start and the day of progesterone rise in NC-cycles / start of progesterone administration in HRT-cycles (+/- 1 - 2 days) will be performed.

Secondary Objectives/research questions

- To evaluate differences (delta) between the mean PI (between right and left A. uterine) and mean RI (between right and left A. uterine) on the day of cycle start and the day of ovulation induction - 1 - 2 days
- To compare thickness of the lining between HRT or NC.
- To compare number of days of estradiol exposure before the embryo transfer between HRT or NC.

Introduction

A. Background:

A wide spectrum of different factors, including uterine receptivity and endometrial thickness (Abdalla et al, 1994; Noyes et al, 1995) and endometrial texture (Bakos et al, 1993), have been implicated as crucial factors in implantation. It has also been suggested that uterine receptivity is related to the uterine blood flow. Due to the availability of ultrasound Doppler measurements, the uterine blood flow can be assessed non-invasively by transvaginal Doppler ultrasonography.

It is also known, that there are remarkable differences in the endocrinological milieu between natural cycles, ovarian stimulation cycles for IVF / ICSI and hormonal replacement cycles. Those differences may lead to different flow pattern in the vessels, providing blood supply to the uterus.

Until now, there are no data whether there is a difference in the blood flow of the aa. Uterinae .

B. Justification:

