- Intake of Aspirin or similar medication which might influence the blood flow
- Status after tubal ligation
- Status after surgery in the adnexal region on 1 side

E. Intervention and Follow-up

- Patient will present themselves on day 2 / 3 of their period.

- Patients will undergo ovarian stimulation for IVF / ICSI in a GnRH-antagonist protocol: Start of stimulation medication (HMG, recFSH) on either day 2 or 3 of the cycle, dosage according to the ovarian response. From day 5 of stimulation a GnRH-antagonist will be added to prevent premature ovulation. Medication for ovulation induction (hCG, GnRH-agonist or dual trigger) will be given when at least 3 follicles are ≥ 17 mm.
- Patients will be planned for FET in either HRT or NC, according to the physician's decision.
- Factors to recommend HRT FET: irregular cycle, PCO, unavailability for treatment monitoring
- Factors to recommend NC FET: regular cycle 28 -33 days, availability for treatment monitoring

Endometrial preparation approaches:**Artificial (HRT) Cycles:**

- Commence E2 4mg from day 2/3 of period for 3 days
- Increase E2 to 6mg on day 4 of E2 treatment. E2 dose may be increased according to clinician discretion based on endometrial thickness.
- The patient will be scanned transvaginally throughout the HRT cycle to not only monitor endometrial development but to also exclude the presence of a dominant follicle on the ovaries.
- In conjunction with ultrasound monitoring the patient will undergo serial measurements of serum LH, estradiol and progesterone levels.
- Commence the initial progesterone dose of 100mg at 22hrs (vaginal suppository) after ≥ 10 days and ≤ 16 days of estradiol administration when the minimal endometrial thickness achieved is 6mm with a trilaminar appearance.
- Subsequently increase progesterone administration to 100mg vaginally three times daily. Continue estradiol administration 6mg (3 tablets daily). Embryo transfer is scheduled 5 days following the initial initiation of progesterone

Spontaneous natural cycles:

- Commencing on the second day of menses and intermittently throughout the patients' natural cycle ultrasound scans will be performed to monitor follicular growth.

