- In conjunction with ultrasound monitoring the patient will undergo serial measurements of serum LH, estradiol and progesterone levels to accurately determine the timing of ovulation. These serum hormonal levels will be measured with an automated Elecsys® immunoanalyzer (Roche Diagnostics, Mannheim, Germany).
- The LH surge will be considered to have begun when the concentration rises by 180% above the most recent serum value and continues to rise thereafter (Irani et al. 2017, Fatemi et al., 2010).
- Day 1 after the LH rise, a decrease in estradiol concentration is identified. Twenty four hours later progesterone concentrations rise with a level of greater than or equal to 1.5nmol /L confirming ovulation (day 0) (Irani et al., 2017; Speroff et al.). This is considered as day 0 with initiation of vaginal progesterone 100mg (vaginal suppository) at 22pm that night. The following day (day 1) the patient increases progesterone administration to 100mg vaginally three times daily (8 hourly) and continues this regime until 7 weeks gestation as per clinic protocol. Embryo transfer is scheduled 5 days (day 5) following confirmation of ovulation (day 0).

For all study arms, transvaginal scan will be performed after the patient had emptied the bladder and is positioned in lithotomic position.

Measurement of the Doppler in the aa. uterinae:

A sagittal section of the uterus will be obtained and the cervical canal and internal cervical os will be identified. The transducer will be gently tilted from side to side and color flow mapping will be used to identify each uterine artery along the side of the cervix and uterus at the level of the internal os. Pulsed wave Doppler will be used with the sampling gate set at 2 mm to cover the whole vessel and care will be taken to ensure that the angle of insonation is less than 30°. When three similar consecutive waveforms are obtained, the PI and peak systolic velocity (PSV) will be measured and the mean PI of the left and right arteries calculated.

Images of the blood flow measurements will be taken and stored in an access-restricted folder. After completion of the study recruitment and data analysis, the images will be destroyed.

Timing for measurement of the Doppler in the aa. Uterinae will be performed:

- Ovarian stimulation cycle: day 2 or 3 of the cycle; day of ovulation induction or 1 to 2 days before in case patient will not be seen directly on the day of ovulation induction
- FET cycle:

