- HRT: day 2 or 3 of the cycle and day of start of progesterone administration or 1 to 2 days before in case patient will not be seen directly on the day when she starts progesterone
- NC: day 2 or 3 of the cycle and day of start of progesterone rise or 1 to 2 days before in case patient will not be seen directly on the day when progesterone starts to rise

F. Collection of biological samples and information

No biological samples will be collected for this study

Statistical methodology

A. Data base

The database will be rigorously defined with the variables destined to be analyzed according to the objectives set. The necessary information will be exported from the clinical information manager, SIVIS, to a table in Excel format through a database-based query system. The data which is not recorded in SIVIS will be collected in a password-coded EXCEL file to guarantee the data protection.

The exported data will be duly codified in order to protect the clinical and personal information of the patients according to the applicable law in the place where the research project is carried out.

Finally, and prior to the statistical study, an exploratory data analysis will be carried out to review the quality of the information extracted.

B. Study Variables

EXPOSURE VARIABLES (INDEPENDENT)

- Type of endometrial stimulation. Categorical dichotomous variable (HRT or natural cycle)

MAIN-OUTCOME MEASURE (DEPENDENT)

- Difference in the blood flow, calculated as PI and RI, between the HRT- and the NC-FET cycles, on the day of progesterone administration / progesterone rise. Quantitative continuous variable

SECONDARY OUTCOME MEASURES (DEPENDENT)

- δ_{S11} : Continuous quantitative variable measured as the differences between average PI value on the day of cycle start and the day of ovulation induction - 1 - 2 days.
- δ_{S12} : Continuous quantitative variable measured as the differences between average RI value on the day of cycle start and the day of ovulation induction - 1 - 2 days.
- Thickness of the lining. Continuous quantitative variable measured in millimeters (mm).
- Number of days of estradiol exposure before the embryo transfer. Discrete quantitative variable.

CONTROL VARIABLES

- Cycles days before start of progesterone administration.
- In HRT cycles: amount (mg) of administered Estradiol.
- Age of the patient
- BMI of the patient
- Number of previous pregnancies
- Number of previous C-sections
- Number of previous miscarriages

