- Smoker status: Smoking yes/no

C. Sample Size

So far, no study has been published evaluating the PI and RI of the arteria uterina between HRT- and NC-FETs.

The study of *Tekay et al.* compared the PI of the arteria uterina in a total of 57 patients in fresh ET's after ovarian stimulation and FET with HRT-preparation of the endometrium. However, this article does not study all the variables of our interest. Besides, it has low statistical power and our populations are different, so we consider that it is more convenient to carry out a pilot study to study descriptively the variables of interest in our population.

As this will be a pilot study, we plan to include 30 patients in each arm (HRT / NC), therefore we would estimate that we will have to include approximately 80 patients in total, as at the time of ovarian stimulation it will not be clear which type of FET patient will undergo later on. This approach was chosen in order not to interrupt patient recruitment. As this is expected to be a 2 : 1 recruitment (HRT : NC), an intra-group homogeneity analysis will be performed and if there are differences, patients from this group will be randomly selected for statistical analysis. Besides, in anticipation of potential participants wishing to withdraw from the study, an additional 5% of patients to the total sample will be added to cover possible losses, recruiting a total of 84 participants.

D. Statistical data analysis

EXPLORATORY DATA ANALYSIS

A statistical summary of the data collected in the study describing patient's population, cycle's most relevant parameters together with clinical results will be provided.

- Categorical variables will be presented in frequency tables, providing absolute frequencies and proportion of each level of each factor in the sample.
- Continuous variables will be summarized according the mean, standard deviation and 95%-confidence interval, all of them will be represented by diagrams or densities quartiles.

Exploratory data analysis will allow evaluating data quality and detecting anomalies.

HOMOGENEITY ANALYSIS

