Although the inclusion criteria and study design tend to preserve the homogeneity of study, it is important to ensure comparability between groups for each control variable. Since each patient is assigned to a group according to clinical criteria and not by random assignment between groups, it will be important to perform a homogeneity analysis to ensure that the effect studied may be due to the type of endometrial preparation and not to the effect that may be caused by a control variable behaving differently between the two study groups.

Consequently, categorical variables will be compared using the χ^2 test, and for quantitative variables, a t-Student test will be applied (if we can assume normality, if it is not possible, we will use the Kruskal-Wallis test).

OBJECTIVE ASSESSMENT

To assess the primary objective, and considering the descriptive nature of any pilot study, confidence intervals of 90%, 95% and 99% will be provided for the blood flow level in each group, and for the difference

between the comparison groups. A basic comparison test will also be provided on an indicative basis. In order to do this, and considering the size of the sample, we will first apply tests of the normality of the data. If these tests are favourable, a t-Student test will be applied. In case of not being able to assume normality, we will apply a non-parametric test.

We will proceed in the same way for the rest of the secondary objectives.

Work plan

Phase I: drafting of protocol ([name], [name], [name]) and review / approval through UAGI and EC approval

Phase II: Patient recruitment and follow-up ([name], [name])

Phase III: Data analysis ([name], designated statistician from UAGI)

Phase IV: Drafting and reviewing of manuscript, submission and publication ([name], [name], [name], [name], [name])

	2019											
	Jan	Feb	Mar	Apr	May	Jun	Jul	Aug	Sep	Oct	Nov	Dec
Phase I												
Phase II												
Phase III												
Phase IV												
Phase V												

	2020											
	Jan	Feb	Mar	Apr	May	Jun	Jul	Aug	Sep	Oct	Nov	Dec
Phase I												
Phase II												
Phase III												
Phase IV												
Phase V												

Ethical issues

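### The stimulation-cycle change in PI and RI inherits the HRT-versus-NC method, although its objective names no such contrast and no pooled within-woman analysis is assigned to it

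*Combined protocol and SAP*

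**What the plan says.** Under Secondary Objectives/research questions, the first item is the difference in mean PI and mean RI "on the day of cycle start and the day of ovulation induction - 1 - 2 days". The next item reads differently: "To compare thickness of the lining between HRT or NC". The third, on days of estradiol exposure, also names the two FET types; the first does not.

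The Doppler timing list in E. Intervention and Follow-up places these measurements: "Ovarian stimulation cycle: day 2 or 3 of the cycle; day of ovulation induction or 1 to 2 days before in case patient". Ovulation induction belongs only to the stimulation cycle, since the natural-cycle FET is spontaneous. B. Study Variables defines δS11 (PI) and δS12 (RI) as the corresponding differences, and lists a single exposure variable, HRT or natural cycle.

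Under OBJECTIVE ASSESSMENT, the primary analysis is that "confidence intervals of 90%, 95% and 99% will be provided for the blood flow level in each group, and for the difference", the latter taken across the comparison groups. An indicative t-Student or unnamed non-parametric test follows. The secondary objectives are then covered by "We will proceed in the same way for the rest of the secondary objectives".

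C. Sample Size explains why more than 60 women are recruited: "at the time of ovarian stimulation it will not be clear which type of FET patient will undergo later on".

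**The concern.** The method carried over is built around two groups, and the only groups the plan defines are HRT and NC. Applied to δS11 and δS12, its contrast and test compare the stimulation change between women who later have one or the other FET type. No objective asks that. The answer would also be hard to interpret, because FET type follows patient characteristics: "Factors to recommend HRT FET: irregular cycle, PCO, unavailability for treatment monitoring".

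The question actually posed, in the Abstract and again under Justification, is whether uterine artery flow changes during stimulation. A difference between groups says nothing about a change they share. The results could therefore show two subgroup intervals and a non-significant test, which a reader might take as no effect of stimulation, with no prespecified estimate in all women to set beside them.

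**Working it through.** **The plan's own figure.** Recruitment of 84 reproduces as 80 × 1.05 = 84. The point does not depend on it. The 30 per arm is a pilot choice with no stated effect size, SD or power.

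**What each objective asks and what the carried-over method supplies**

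| Secondary objective | HRT/NC contrast named? | Does the between-group contrast answer it? |
|---|---|---|
| Change in PI and RI during stimulation | No | No; only the per-group intervals bear on it |
| Endometrial thickness | Yes | Yes |
| Days of estradiol exposure | Yes | Yes |

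**Why a common change cancels.** Let the mean change be μ + a in later HRT women and μ + b in later NC women. The between-group contrast estimates (μ + a) − (μ + b) = a − b, and μ drops out. In a simulation of 20,000 runs at 30 versus 30, with the same change in both groups, the two-sample test rejected in 4.8% of runs (change of 0.3 SD) and 5.2% (0.5 SD), which is its 5% level. A pooled paired test at n = 80 has power of about 76% and 99% for the same changes. The values 0.3 and 0.5 SD are assumptions, since the documents give no expected change.

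**Precision.** The unit is the SD of the within-woman change, which the documents do not give; it is assumed similar in both groups, with normal changes. The expected 2:1 recruitment applied to 80 women gives 80 × 2/3 ≈ 53 HRT and 80/3 ≈ 27 NC.

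The 95% half-width for a mean change is t(0.975, n − 1)/√n:

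- pooled, n = 80: 0.223
- HRT, n = 53: 0.276, which is 0.276/0.223 = 1.24 times the pooled value
- NC, n = 27: 0.396, which is 0.396/0.223 = 1.78 times the pooled value

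The 95% half-width for the difference between groups is t(0.975, n₁ + n₂ − 2) × √(1/n₁ + 1/n₂), which at 53/27 is 0.471. That interval is both wider and for a different quantity.

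If the study instead analyses exactly 30 per arm, the same 60 women give 0.258 pooled, against 0.373 in each group.

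**Does pooling need equal changes in the two groups?** No. If the group means differ by d (in SD units), the total SD is √(1 + p(1 − p)d²), with p = 53/80. For d = 0.3 it is 1.010 (half-width 0.225); for d = 0.5 it is 1.028 (half-width 0.229). The pooled mean is then the average change over the recruited mix.

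**The case against.** The strongest reply is that the plan already answers this objective. δS11 and δS12 are defined as within-woman differences. The carried-over intervals in each group, applied to them, estimate within-woman change. EXPLORATORY DATA ANALYSIS promises a mean, SD and 95% interval for continuous variables, which could well include a whole-cohort figure for each delta. A pooled mean can also be rebuilt from the group sizes, means and SDs. All of this stands, so a reader who infers that the stimulation question goes unanswered, or that no within-woman estimate exists, goes further than the documents support. What remains is that the general summary is not tied to this objective, does not give the 90% and 99% levels, and carries no test.

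A second reply is that t-Student is not labelled unpaired, so the carried-over sentence could mean a comparison of the two days. That reading is possible. It is the less natural one, because the method speaks of groups and the only groups defined are HRT and NC. The text therefore does not show that a wrong test is definitely planned. It shows that the likelier reading gives the less useful one.

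Third, tests in this pilot are indicative only, and HRT versus NC is the primary aim. Both are true, and both limit the weight of the point.

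**Conclusion.** The point holds as a minor one. A stated rule sends a within-woman, whole-cohort question through a two-group method. On its most natural reading, the contrast and test address something no objective asks and are blind to a change common to both groups. The objective is answered in part by subgroup intervals and perhaps by a general summary, but no pooled estimate or within-woman test is named as its analysis.

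The size is a 95% half-width of 0.22 SD pooled, against 0.28 and 0.40 SD by group. This rests on an assumed 53/27 split of 80 women and similar SDs of the change in the two groups. A reader might infer that both group intervals must be wider than the pooled one, but that depends on the SDs: if the larger group's SD were 0.8 of the overall SD, its half-width would be 0.8 × 0.276 = 0.221, level with 0.223.

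Nor do the documents say that the conditional random selection in C. Sample Size would be applied to the stimulation data. They leave its scope open, so no loss of data should be claimed from it.

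**What to change.** Under OBJECTIVE ASSESSMENT, limit the carried-over method to endometrial thickness and days of estradiol exposure, and add:

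> Delta PI and delta RI in the stimulation cycle are calculated per woman and analysed in all included women with both stimulation-cycle measurements, pooled over later FET type and without the random selection used to balance the FET groups. The mean change is given with 90%, 95% and 99% confidence intervals, with a paired t-test or Wilcoxon signed-rank test as the indicative test. Deltas by HRT/NC are descriptive only.

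The cost is two or three sentences in the analysis section, best added before the data are analysed. It needs no new data, visits or patients, and the HRT-versus-NC method stays where the objectives call for it.
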